2.1.6 Study medication

The study consists of three treatment periods.

In Period 1 patients will be randomized to metformin + vildagliptin 50mg bid, or metformin + placebo. If initial treatment fails to maintain HbA1c < 7.0%, confirmed at two consecutive scheduled study visits (after remapping in [section 1.3.3](#) has been applied), starting from Visit 4 (Week 13), then vildagliptin will be added to metformin in the metformin-only arm in Period 2. The Period 1 end date is defined as the date of the second of the two consecutive scheduled study visits, i.e. the initial treatment failure date. The Period 2 start date is defined as the next day.

In Period 3, insulin is considered based on local guidelines. Both patients and investigators will remain masked to the treatment allocation in Period 1, and the study will compare the two different treatment approaches. The Period 3 start date is defined as the date of insulin initiation. The Period 2 end date is defined as the previous day.

Treatments are referred to as ‘Treatment approach’ throughout this analysis plan to acknowledge that patients are not on the same treatment for the duration of the study. When summaries are detailed for the ‘Treatment Period’, they will include data from Periods 1, 2 and 3, unless specified otherwise.

The duration of exposure to study medication (in months) during the treatment period will be computed for all patients using the algorithm outlined in [Section 1.4](#) and summarized by treatment approach for the RAN both descriptively (i.e., mean, standard deviation, median, minimum and maximum) and by 3 - monthly intervals (0 - < 3 months, 3 - < 6 months, ..., ≥ 60 months).

The study Period 1 duration (in months) will be also similarly summarized for the RAN. The study Period 1 duration is defined as (initial treatment failure date – treatment start date + 1)/30.4375 for patients who entered study Period 2. The study Period 1 duration is the same as overall study duration for patients who did not enter into Period 2.

The study period from treatment start to the end of Period 2 will be computed for all patients who initiate insulin in Period 3 and for patients discontinuing the study in Period 2 due to being unable or unwilling to initiate insulin for treatment intensification in Period 3. The duration will be defined as (initiation date of insulin – treatment start date)/30.4375 for patients who initiate insulin, and (last study drug date – treatment start date + 1)/30.4375 for patients who do not enter Period 3.

Total subject year exposure (SYE) will also be summarized by treatment approach for the RAN. SYE (years) for each treatment will be calculated as (duration of exposure in days, disregarding any treatment interruptions, for all subjects in that treatment approach) / 365.25. For patients who did not take any study medication, the exposure is set to zero. This summary will be repeated on Period 1 data only, and also on Vildagliptin exposure only.

Study medication information will be listed for the RAN, including information about vildagliptin, placebo, metformin and insulin use.

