3.1.2 Period 1: vildagliptin/metformin combination versus metformin

At Visit 3, patients will be randomised 1:1 to one of the following study regimens:

- Metformin up to 1000mg bid plus vildagliptin 50mg bid or
 - Metformin up to 1000mg bid plus matching placebo bid.
- 

During the first 4 weeks of Period 1 the metformin dose can be adjusted (increased or decreased, but not below 1000mg daily or above 2000mg). An unscheduled visit can be performed in order to adjust the metformin dose if deemed necessary. The objective is to optimise metformin dose to 2000mg daily or to the maximum tolerated dose. Patients who are unable to tolerate a total daily dose of 1000mg metformin will be discontinued. The metformin dose at week 4 post-randomisation and the vildagliptin 50mg bid or matching placebo bid dose should remain unchanged throughout the duration of the study, except for AEs or untoward events that may require dose reduction or interruption (see [Section 5.5.5](#)).

Any anti-diabetic medication other than the study drug regimen is not allowed during Period 1, except if the patient had temporarily reduced/interrupted the treatment regimen due to AEs or untoward events that require temporary dose adjustments. In such cases dose adjustments or interruptions of the study drug are permitted (see [Section 5.5.5](#)). Patients who, during Period 1, take anti-diabetic medication other than the study drug regimen (except for AEs or untoward events that require temporary dose adjustments, see [Section 5.5.5](#)) will be discontinued from the study.

The duration of Period 1 may differ between patients depending on the time when the second of two HbA1c measurements taken at two consecutive visits after randomisation ([Table 6-1](#) & [Table 6-2](#)) confirms HbA1c $\geq 7.0\%$.

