3.1.3 Period 2: vildagliptin/metformin combination versus vildagliptin add-on to metformin

In the case of two consecutive HbA1c measurements $\geq 7.0\%$ from two consecutive study visits during Period 1, scheduled according to [Table 6-1](#) & [Table 6-2](#), patients in both arms will receive new vildagliptin study medication packs. The investigator will contact the IRT system within 2 weeks after the receipt of the second of the two elevated HbA1c measurements. The IRT system will assign the new vildagliptin study medication packs. Patients who were randomised to the placebo arm in Period 1 will now receive vildagliptin 50mg bid. Patients who were randomised to the active vildagliptin 50mg bid arm in Period 1 will continue to receive vildagliptin 50mg bid. All patients will continue to take their metformin dose unchanged. Period 2 will remain masked to the patient and both patients and investigators will remain masked to the treatment allocation in Period 1.

Any anti-diabetic medication other than the study regimen is not allowed during Period 2, except if the patient had temporarily reduced/interrupted the treatment regimen due to AEs or untoward events that require temporary dose adjustment/interruption (see [Section 5.5.5](#)).

If, during Period 2, therapy intensification is required in accordance with the local guidelines, the patient will enter Period 3.

The duration of Period 2 may differ between patients. End of Period 2 is considered when insulin treatment is initiated, or alternatively when the patient is discontinued because insulin treatment is not initiated in Period 3 (see [Section 3.1.4](#)).

[figure not shown]

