9.3 Treatments (study drug, rescue medication, other concomitant therapies, compliance)

The duration on the study medication (in weeks) during the overall randomised treatment period will be computed for all patients using the following algorithm:

(last study drug date – Visit 3 date)/7 or

(last study visit date – Visit 3 date + 1)/7 if the last study drug date is missing or incomplete.

Duration will be set to 0 for patients who did not take any study drug.

The above defined duration will be summarised according to the treatment patients are assigned to at randomization for the RAN set both descriptively (i.e., mean, standard deviation, median, minimum and maximum) and by duration category (≥ 0 and < 13 weeks, ≥ 13 and < 26 weeks..., in 13-week intervals cumulatively up to ≥ 260 weeks).

The study Period 1 duration (in weeks) will be also similarly summarised in the RAN set. The study Period 1 duration is defined as (initiation date of new study vildagliptin packs due to treatment failure – visit 3 date)/7 for patients who entered study Period 2. The study Period 1 duration is the same as overall study duration for patients who did not enter into Period 2.

The study period from randomization to the end of Period 2 will be computed for all patients who initiate insulin in Period 3 and for patients discontinuing the study in Period 2 due to being unable or unwillingness to initiate insulin for treatment intensification in Period 3.

Prior and concomitant therapies taken during the randomised double-blind period will be summarised by ATC class and preferred term according to the treatment patients are assigned to at randomization in the RAN set.

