9.5.2.2 Statistical analysis methods

[figure not shown]
[figure not shown]
Rate of loss in glyceimic control over time

The rate of loss in glyceimic control over time will be estimated by the slope of HbA1c over time (in years) as a random coefficient in a linear mixed effect model: the model will be fitted to HbA1c data collected from Week 26 and onwards, up to and including the end of the Period 1 visit, i.e. up to and including the initial treatment failure date. It includes treatment approach, geographic region, baseline HbA1c, time (of HbA1c measurements, in years) and the interaction of treatment approach by time as the fixed effects, and time and intercept as a random effects. Treatment approach and geographic region will be considered as classification variables while baseline HbA1c and time are the covariates. The unstructured covariance will be used as the covariance structure within patients. The actual hypothesis will be tested using the treatment approach by time interaction term. Note that it is not an issue that patients who ‘fail’ at Week 26 will only contribute one data point to the analysis, as this is expected in only a few patients.

The mean slopes within each treatment approach and the difference in mean slopes between two treatment approaches as well as the p-value obtained from the test using the above model will be presented. Graphical representation will also be produced as required.

The analysis will be performed using the FAS. It will be performed in the PPS as supportive analysis as well.

The assumptions for inference using the model as described above (i.e., errors are independently normally distributed with constant variance) will be checked using CSR Section 16 table(s) by subjective examination of the presented residual plots: normal probability plot and residuals versus fitted values plots.

Variables related to the rate of loss in glycemetic control over time

The rate of loss in glycemetic control in FPG from 26 weeks to the end of Period 1 will be assessed using the same random coefficient linear mixed effect model as used in the analysis of ‘rate of loss in glycemetic control in HbA1c from Visit 5 (Week 26) to the end of Period 1’. This analysis is performed in the FAS only.

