An analysis of covariance (ANCOVA) model with treatment, geographic region as classification variables and BL value as a covariate will be used to assess all secondary efficacy variables related to change from BL to endpoint. The least squares mean (“adjusted mean”) change from BL for each treatment group, the difference in the least squares mean changes between the two treatment groups, and the two-sided adjusted 95% confidence interval along with the p-value for the difference will be obtained from this analysis model and presented.

The endpoint is defined differently for these secondary endpoints as follows.

- For change in AUC of ISR/G, OGIS, [REDACTED] [REDACTED] from BL to EOS, the endpoint is defined as the final available post-randomization assessment obtained at any visit (scheduled or unscheduled) up to final [REDACTED]

scheduled study visit (Visit 23, Week 260).

- For change in AUC of ISR/G, OGIS, [REDACTED] from BL to end of Period 2 (see [Section 3.1.3](#)), the endpoint is defined as the final available post-randomization assessment obtained at any visit (scheduled or unscheduled), prior to or at the initiation of insulin therapy, up to final scheduled study visit (Visit 23, Week 260).
- For change in AUC of ISR/G, OGIS, [REDACTED] from BL to initial treatment failure, the endpoint is defined as the final available post-randomization assessment obtained at any visit (scheduled or unscheduled), prior to or at the start of additional new vildagliptin medication package use due to initial treatment failure, up to final scheduled study visit (Visit 23, Week 260).

Note that for meal-test related parameters (AUC of ISR/G and OGIS), the above analyses will be performed only when sufficient patient's data warrant such analyses.

Supportive descriptive analysis for secondary [REDACTED] variables over time

Summaries of absolute values and change from BL to end of Period 1 in secondary or exploratory variables (including FPG, [REDACTED], AUC of ISR/G, OGIS, [REDACTED]) by treatment group and visit will be presented in the FAS.

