2.3.1 Overall experience of adverse events (AEs)

The number and percentage of patients reporting any adverse event during the treatment period of the study will be summarized by primary system organ class, preferred term and treatment approach overall (including study periods 1, 2 and 3) and by study period. Percentages will be based on the number of patients in the SAF per treatment approach and study period. An AE will be assigned to a period if its start date is after or on the start date but not later than the end date of that period. All AEs will be assigned to a specific study period – if it is not possible to assign an AE into a specific study period of the patient based on the AE start date, then the event will be assigned to the last study period started by the patient. This will ensure that all AEs will be categorized to a specific study period

The most common adverse events reported ($\geq 2\%$ in any group) during the treatment period of the study will be presented in descending frequency starting from the most common event in a Text Table. A complete table of all events reported in descending frequency will be prepared..

Adverse events that were suspected to be related to study drug will be summarized. Note that if the relationship to study drug is missing for any adverse event, then that adverse event will be assumed to be related to study drug.

The maximum severity of all adverse events during the treatment period of the study will be summarized. Note that if the severity is missing for any adverse event, then that adverse event will be assumed to be severe.

An overall summary of the number and percentage of patients with drug-related AEs, severe AEs, AEs with outcome of death, SAEs and adverse events leading to permanent discontinuation of treatment will be presented by study period and treatment approach.

The number and percentage of patients reporting any adverse event during the treatment period of the study will be summarized by standardized MedDRA query (SMQ) level and treatment approach as well.

In addition, the number and percentage of patients reporting any adverse event during the treatment period will also be summarized by primary system organ class, preferred term, treatment approach and age group (as defined in section 2.1.5)) overall and by treatment period..

Note that there will be no AE adjudication for this study.

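### The SAP starts Period 2 the day after the failing visit, before new packs can be issued, so metformin-arm AEs that begin on placebo are tabulated under Period 2 and leave the Period 1 safety analyses

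*SAP*

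**What the plan says.** SAP 2.1.6, identical in V3.0 and Addendum 1, sets the boundary by visit date: "The Period 1 end date is defined as the date of the second of the two consecutive scheduled study visits". It continues: "The Period 2 start date is defined as the next day". Period 1 duration in the same section also runs to the failure date. SAP 2.3.1 sorts adverse events by these dates: "An AE will be assigned to a period if its start date is after or on the start date" and no later than the period's end date.

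The protocol has two anchors.

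- **Pack date.** Section 9.3 ends Period 1 duration at the "initiation date of new study vildagliptin packs due to treatment failure". In 9.5.2.2, the endpoint for change from baseline to initial treatment failure is the last assessment "prior to or at the start of additional new vildagliptin medication package use due to initial treatment failure".
- **Failing visit.** The slope model in 9.5.2.2 uses HbA1c data "up to and including the end of the Period 1 visit, i.e. up to and including the initial treatment failure date". Section 3.1.2 leans the same way: "The duration of Period 1 may differ between patients depending on the time when the second of two HbA1c measurements" confirms the threshold.

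On the switch itself, protocol 3.1.3 says: "The investigator will contact the IRT system within 2 weeks after the receipt of the second of the two elevated HbA1c measurements". The IRT then assigns the packs, and only with these does the placebo arm move to vildagliptin.

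**The concern.** HbA1c is measured at a central laboratory (protocol 6.4.1), so the site must wait for the confirming value, and new packs follow the IRT contact. A Period 2 that begins the day after the visit therefore begins, in the metformin arm, on placebo.

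This matters for safety because Period 1 is the only period in which the arms take different drugs. SAP 2.3 repeats key safety analyses on Period 1 data. SAP 2.3.1, 2.3.1.1 and 2.3.5 tabulate AEs, deaths, SAEs, predefined risks and hypoglycemia by period, and SAP 2.3.5 plans a conditional chi-square test of hypoglycemia in Period 1. A metformin-arm event in the gap occurs on the Period 1 regimen but is counted in the add-on period. SAP 2.8 does not list the change from the protocol 9.3 formula, although it lists one-day changes to the exposure formula.

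**Working it through.** **1. Which date each text uses**

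| Text | Anchor for the end of Period 1 |
|---|---|
| SAP 2.1.6, 1.2 and 2.2.3.3 | second failing visit |
| Protocol 9.5.2.2, slope model | second failing visit |
| Protocol 3.1.2 | confirming HbA1c |
| Protocol 9.3, Period 1 duration | initiation of new packs |
| Protocol 9.5.2.2, change-from-baseline window | start of new packs |

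**2. Length of the gap**

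Gap = laboratory turnaround (not stated) + time to IRT contact (at most 14 days after receipt) + dispensing time (not stated). Only the middle term is bounded. I assume 7 to 28 days in total.

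**3. Metformin-arm failures**

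The documents give no figure for the gap, so there is nothing to reproduce. Inputs from protocol 9.6 and SAP 2.7: n = 1000 per arm; 10% initial failures at 13 weeks (0.25 year); failure rate λ = 0.071 per year; five years; dropout μ = 0.11 per year (protocol, SAP Addendum 1) or 0.04 (SAP V3.0). Rates are treated as exponential.

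- Initial failures = 1000 × exp(−0.25μ) × 0.10
- Later failures = 1000 × exp(−0.25μ) × 0.90 × λ/(λ+μ) × [1 − exp(−4.75(λ+μ))]

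μ = 0.11: 97 + 198 = 295. μ = 0.04: 99 + 234 = 333.

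**4. Period 2 time in that arm**

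Initial failures enter Period 2 at 0.5 year (second of Weeks 13 and 26) and contribute (1 − exp(−4.5μ))/μ years each. A later failure at time t contributes (1 − exp(−μ(5−t)))/μ, integrated over the failure times. No exit to insulin is assumed. Totals: 795 patient-years (μ = 0.11) and 973 (μ = 0.04).

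**5. Placebo time inside SAP Period 2 = failures × gap days / 365.25**

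| Gap | μ = 0.11 | Share of 795 | μ = 0.04 | Share of 973 |
|---|---|---|---|---|
| 7 days | 5.7 | 0.7% | 6.4 | 0.7% |
| 14 days | 11.3 | 1.4% | 12.7 | 1.3% |
| 21 days | 17.0 | 2.1% | 19.1 | 2.0% |
| 28 days | 22.6 | 2.8% | 25.5 | 2.6% |

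Period 1 duration per failing patient differs between the two definitions by 7/30.4375 = 0.2 to 28/30.4375 = 0.9 months.

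**6. A case outside this range**

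SAP 2.2.2.2 counts a failure when Visits 4 and 6 are high and Visit 5 is missing. Protocol 3.1.3 switches on two consecutive study visits, so a site need not have switched at Visit 6. Such a patient could stay on placebo in SAP Period 2 until a further scheduled visit, 13 weeks later. The documents do not allow a count of these patients.

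**The case against.** The strongest reply is that the SAP chose one of two readings that the protocol already contains. The protocol never gives a Period 2 start date as such: 9.3 defines a duration summary and one part of 9.5.2.2 an endpoint window, while the slope model and 3.1.2 point to the failing visit. This stands. A reader might infer that the SAP contradicts a settled protocol rule, and the documents do not support that.

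A reader might also infer that placebo time is counted as vildagliptin exposure, or that events change arm. Neither is shown. SAP 2.3 tabulates by treatment approach, so a gap event stays with placebo + metformin. The vildagliptin-only exposure summary in SAP 2.1.6 has no stated metformin-arm start date and could already rest on dose records.

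Nor are early events on the new drug lost. The misplaced time lies wholly before the switch, and everything after the new packs start is in Period 2 under either definition.

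The effect is also small, the gap length is assumed, most of the tables concerned are descriptive, and SAP 2.2.2.2 expects missing visits to be rare. All of this limits the size. It does not answer the core point: a written rule places events that began on placebo in the add-on period and removes them from the Period 1 comparison.

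**Conclusion.** The concern holds as a date-definition fault in the by-period safety and exposure derivations of the metformin arm. Under the plan's failure inputs and an assumed gap of 7 to 28 days, about 6 to 25 patient-years on placebo fall in SAP Period 2, or 0.7 to 2.8% of that arm's Period 2 time. The share would be somewhat higher if patients leave for insulin, since the denominator ignores that exit. The upper end is not a bound, because laboratory and dispensing times are not given and failures counted across a missing visit can last longer.

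The vildagliptin arm takes the same drug on both sides of the boundary. The primary endpoint is unaffected, since its event time is the second failing visit in both documents. SAP 2.8 mentions the Period 1 end date only as the reason for another change and does not declare a departure from protocol 9.3. The point is worth correcting because it touches the one period with a randomised drug contrast and the correction is cheap.

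**What to change.** 1. Keep the failing visit as the event date and as the end-of-Period-1 anchor for all efficacy analyses, including the HbA1c and FPG slopes and the 26-week origin in Period 2. Moving that origin to the pack date would put it past the scheduled 13-weekly visit.
2. For by-period AE and hypoglycemia tables, Period 1-only safety analyses, and Period 1 and vildagliptin-only exposure, start Period 2 at initiation of the newly assigned packs. Use the IRT dispensing date where the first-dose date is not recorded. A patient counted as failing across a missing visit but not switched then stays in Period 1 for safety.
3. Reconcile protocol 9.3 and both parts of protocol 9.5.2.2 with SAP 2.1.6, and list the departure from protocol 9.3 in SAP 2.8.

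Cost: SAP wording and one derivation. The IRT records kit assignments (protocol 5.5.2, 8.3), and protocol 9.3 already presupposes an initiation date. It is not certain that the dosage record holds the first dose of a masked pack at an unchanged dose, hence the fallback. Safety and efficacy period boundaries will differ slightly and need a footnote.

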2.1.7 Concomitant medication

Concomitant therapies taken during the treatment period will be summarized by anatomical therapeutic chemical classification system (ATC) class and preferred term according to the treatment approach patients are assigned to at randomization in the RAN. The number and percentage of randomized patients (RAN) in each class and preferred term will be tabulated by treatment approach. This summary will be repeated on period 1 data only, i.e. concomitant therapies taken during Period 1.

Use of anti-diabetic medications prior to study entry (as recorded on the eCRF) will be summarized by ATC class, preferred term and treatment approach.

The duration and average daily dose of metformin taken during the screening and run-in period will be summarized descriptively (mean, standard deviation, median, minimum and maximum), using data from 35 days prior to screening through to 35 days after randomization. This will be based on information collected on the i) Metformin dosage administration page of the eCRF (considering only dosages which are at most 35 days after randomization); and ii) information collected on the prior anti-diabetic medication eCRF page with a preferred term containing 'METFORMIN' and a dose of 'mg' (considering only dosages which are at most 35 days prior to the screening visit). The average daily dose of metformin during this window will also be summarized categorically (<2000 mg, ≥2000 mg).

Listings of concomitant medications and prior anti-diabetic medications will be presented by treatment approach and patient number.

